3.1 Eligibility Criteria

3.1.1 Lower risk MDS patients (IPSS-R score ≤ 3.5 at diagnosis) who have progressed or are refractory to/intolerant of prior therapy and meet one of the following categories:

- RBC transfusion dependent according to IWG criteria must either be unresponsive to prior ESA therapy or have an EPO level > 500
- Prior HMA therapy
- Patients with the following cytopenias who otherwise are felt to require treatment per the treating physician:
 - Platelets $< 50k/uL$
 - ANC < 500 cells/uL
- Patients with MDS with isolated del(5q) (“5q- syndrome”) must have progressed on or not tolerated lenalidomide
- Patients who are not felt to be candidates for or lack other standard treatment options. Patients with prior luspatercept exposure are eligible.
- Patients with dysplastic type CMML (WBC $< 13,000$ cells/uL) meeting the above criteria are eligible; responses will be assessed using MDS criteria

3.1.2 Age ≥ 18 years. Because no dosing or adverse event data are currently available on the use of MGB453 in participants < 18 years of age, children are excluded from this study, but will be eligible for future pediatric trials.

3.1.3 ECOG performance status ≤ 2 (see Appendix A).

3.1.4 Participants must have adequate organ and marrow function as defined below within 21 days of treatment:

- Total bilirubin ≤ 2 mg/dL (unless due to Gilbert’s in which case it must be < 3 mg/dL)
- AST(SGOT)/ALT(SGPT) $\leq 3 \times$ institutional ULN
- Creatinine clearance ≥ 30 mL/min/1.73 m² (by MDRD calculation)

3.1.5 Human immunodeficiency virus (HIV)-infected participants on effective anti-retroviral therapy with undetectable viral load over the prior 6 months are eligible for this trial.

3.1.6 Participants with known history or current symptoms of cardiac disease, or history of treatment with cardiotoxic agents, should have a clinical risk assessment of cardiac function using the New York Heart Association Functional Classification. To be eligible

for this trial, participants should be class 2B or better.

3.1.7 Ability to understand and the willingness to sign a written informed consent document.

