6. DOSING DELAYS/DOSE MODIFICATIONS

MBG453 may be delayed due to toxicities. Doses may be delayed for up to 28 days for toxicity; toxicities that result in more than 28 days delay should result in discontinuation from the study medication. Patients that are deriving clinical benefit but require a treatment delay beyond 28 days for non-toxicity events should be discussed with the principal investigator.

Dosing may be resumed once an AE has resolved to baseline or to Grade 1. If a treating investigator considers it in the patient's best interest to resume therapy before resolution of an AE or to resume without dose modification this may be considered on a case-by-case basis after discussion with the overall PI of the trial.

Dose modifications of MBG453 may be accomplished through dose reduction or altering the treatment interval; provisional dose levels are shown below.

Dose delays and modifications will be made as indicated in the following table(s). The descriptions and grading scales found in the revised NCI Common Terminology Criteria for Adverse Events (CTCAE) version 5.0 will be utilized for dose delays and dose modifications. A copy of the CTCAE version 5.0 can be downloaded from the CTEP website

http://ctep.cancer.gov/protocolDevelopment/electronic_applications/ctc.htm.

Dose Level	Dose
-2	240 mg every 28 days
-1	400 mg every 28 days
0	800 mg every 28 days

If the patient experiences an AE meeting the criteria for DLT as outlined in section 5.4, including events outside the DLT period, treatment should be held. Patients may resume treatment after resolution to Grade 1 or to the patient's baseline value. If this event occurs during the first cycle (whether or not they are among the first 6 patients being evaluated for DLT assessment) a dose modification must be made. If this event occurs after the first cycle the patient may resume at the same or a lower dose at the discretion of the investigator. Specific guidance is provided below.

Infusion Reaction	Management/Next Dose for MBG453
≤ Grade 1	Decrease infusion rate until recovery
Grade 2	Stop Infusion. Before restarting, pre-medicate according to local institutional guidelines. Restart infusion at 50% of previous rate under continuous observation. Ensure that there is a minimum observation period of 1 hour prior to restarting the infusion(s). If the AE recurs at the reinitiated slow rate of infusion, and despite oral pre-medication, then discontinue treatment
Grade 3	Discontinue treatment

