*Participants requiring a delay of >28 days should go off protocol therapy. **Participants requiring > two dose reductions should go off protocol therapy.	
Recommended management: assess for other causes, empiric corticosteroids, assessment of immune-related organ dysfunction as indicated	

Other Immune-Related Toxicities	Management/Next Dose for MBG453
≤ Grade 1	Continue treatment
Grade 2	Hold until ≤ Grade 1. Resume at same dose level.
Grade 3 lasting < 7 days	Hold* until < Grade 2. Resume at one dose level lower, if indicated.**
Grade 3 lasting > 7 days	Discontinue protocol therapy

Other Immune-Related Toxicities	Management/Next Dose for MBG453
Grade 4	
*Participants requiring a delay of >28 days should go off protocol therapy. **Grade 3 imAEs that do not improve within 7 days on steroids should come off protocol therapy. Consideration should be given for additional immunosuppression. Participants requiring > two dose reductions should go off protocol therapy.	
Recommended management: assess for other causes, empiric corticosteroids, assessment of immune-related organ dysfunction as indicated (e.g. thyroid testing, pituitary testing, GI/pulmonary evaluation, neurological assessment).	

Non-Hematologic Toxicities	Management/Next Dose for MBG453
≤ Grade 1	No change in dose
Grade 2	Hold until ≤ Grade 1. Resume at same dose level.
Grade 3	Hold* until < Grade 2. Resume at one dose level lower, if indicated.**
Grade 4	Off protocol therapy
*Participants requiring a delay of >28 days should go off protocol therapy. **Participants requiring > two dose reductions should go off protocol therapy.	
Recommended management: assess for other underlying/secondary causes	

Hematologic Toxicities	Management/Next Dose for MBG453
≤ Grade 1	No change in dose
Grade 2	No change in dose
Grade 3	Hold* until < Grade 2 (or baseline if baseline was grade 2). If persistent cytopenia beyond day 42 of the cycle, or as indicated, evaluate with a bone marrow biopsy. Resume at one dose level lower, if indicated.**
Grade 4	Hold* until < Grade 2 (or baseline if baseline was grade 2). If persistent cytopenia beyond day 42 of the cycle, or as clinically indicated, evaluate with a bone marrow biopsy. If no evidence of MDS, discontinue therapy.
*Participants requiring a delay of >28 days should go off protocol therapy. **Participants requiring > two dose reductions should go off protocol therapy.	

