
a: Albumin, alkaline phosphatase, total bilirubin, direct bilirubin, bicarbonate or CO₂, BUN, calcium, chloride, creatinine, glucose, LDH, phosphorus, potassium, magnesium, total protein, SGOT [AST], SGPT [ALT], sodium, uric acid, amylase, lipase.
 
b: Serum pregnancy test (women of childbearing potential, WOCP). At screening, a serum pregnancy test (serum β-HCG) must be performed within 3 days before the first dose for WOCP. During the study, a urine / serum pregnancy test should be done at Day 1 of each cycle for WOCP (except Cycle 1 if a pregnancy test had been performed within 72 hours of the first dose) and at EOT visit. A pregnancy test (serum or urine) should be performed every month during the safety follow-up period for WOCP (until day 150). If the patient is not coming to the clinic during the safety follow-up, it can be performed at home or at a local doctor's office, and the results will be communicated to the site staff.
 
c: Bone marrow biopsy and aspirate should be performed at baseline, cycle 3 day 1 ±3 days, and then within 7 days of cycle 5 day 1, at end of treatment, and as clinically indicated. Standard institutional testing including cytogenetics and molecular testing is recommended.
 
d: Off-treatment evaluation. The in-person visit has a window of ±3 days; additional safety follow-up is required through day 150. Note: for IND/IDE trials, follow up visits or other contact are required in order to identify SAEs during the 30 days following the end of study treatment. After end of treatment visit, patients should be followed per section 5.7 for survival and progression.
 
e: Bone marrow assessment for cycle 7 and cycle 11 may be done up to 7 days prior to the start of the treatment cycle. If a patient has a bone marrow assessment within 1 cycle of the planned assessment (e.g. cycle 6 or cycle 10) this may be used for the study assessment. A bone marrow for research samples will be performed on cycle 1 day 3 (window day 3-6).
 
f: Bone marrow samples for correlative studies will be collected at baseline, at cycle 3 day 1, and EOT for both NGS testing and for cytof analysis.
 
g: Blood pressure, heart rate, and temperature will be performed at screening and then as clinically indicated. . Bone marrow biopsy on cycle 5 day 1 will only require Cytof samples to be obtained.
 
h: On C1D1, total bilirubin, direct bilirubin, creatinine, SGOT [AST], SGPT [ALT], and INR should continue to meet inclusion criteria. Baseline values will be those assessed on C1D1
 
i: Follow up to evaluate for progression and survival may be ±7 days from those noted (day 30, 150, 250, and 1 year). Safety evaluations must be through 150 days after the last dose of MBG453. The safety follow up can be done by telephone call or visit. The information collected is kept as source documentation. All SAEs reported during this time period must be reported as described in Section 7.3. Documentation of attempts to contact the subject should be recorded in the source documentation.
 
j: TSH, free T3, and free T4 should be obtained during screening. TSH should be monitored regularly (at selected visits) during treatment and as clinically indicated. If TSH is abnormal, then test free-T3 and free-T4.
 
k: Rapid Heme Panel for NGS should be collected as part of standard of care with bone marrow biopsies at screening, C3D1 (+/-3 days), and EOT/progression. In the event of a dry tap, peripheral blood may be substituted.
											

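### The hematologic hold rule in the Section 6 table omits baselines worse than grade 2 and conflicts with the Section 6 text; two grade labels in the Section 6 tables are also wrong

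*Combined protocol and SAP*

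**What the plan says.** **Hematologic rows.** In the Section 6 Hematologic Toxicities table, the grade 3 and grade 4 rows both say "Hold* until < Grade 2 (or baseline if baseline was grade 2". The footnote adds: "Participants requiring a delay of >28 days should go off protocol therapy". The grade 4 row continues: "If persistent cytopenia beyond day 42 of the cycle, or as clinically indicated, evaluate with a bone marrow biopsy", then "If no evidence of MDS, discontinue therapy".

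**General text.** Earlier in Section 6: "Dosing may be resumed once an AE has resolved to baseline or to Grade 1". For events meeting DLT criteria, Section 6 says "Patients may resume treatment after resolution to Grade 1 or to the patient's baseline value", and Section 5.2.2 is to the same effect. Section 6 also says that delays and modifications follow its tables, and the paragraph on DLT-type events ends by pointing to the guidance below it. Resuming before an AE has resolved is possible as an individual exception agreed with the overall PI.

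**Who is enrolled.** Section 3.1.1 admits patients needing treatment for platelets below 50k/uL or for "ANC < 500 cells/uL". Neither the organ-function criteria (Section 3.1.4) nor the cycle 1 day 1 criteria (Section 5.2.1) set a minimum count. Footnote h of the Section 10 calendar says "Baseline values will be those assessed on C1D1"; it concerns chemistry and INR, so it only supports the point.

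**Labels.** In the GI table, grade 1 (continue) is fewer than 4 stools a day, grade 2 (hold) is fewer than 4 over baseline, and grade 3 is more than 6 over baseline. In the neurological table, grade 3-4 is described by creatinine above 6 times ULN, which is the grade 4 entry in the renal table.

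**The concern.** The trial deliberately enrols patients with severe cytopenias, and Section 2.3 states a particular interest in neutrophil and platelet responses. The table's baseline exception stops at grade 2, so it leaves out the patients for whom a baseline exception matters most. One site could redose a patient who is back at the entry count, relying on the text. Another could follow the table, keep holding, and remove the patient from therapy once the delay passes 28 days.

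The two labels sit in tables that staff use to decide whether to continue, hold or stop an immune checkpoint inhibitor. A GI row that repeats its neighbour's threshold, and a neurological row with no neurological criterion, invite inconsistent handling of toxicity.

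**Working it through.** No sample size or error rate enters this point, so the check sets the rules side by side.

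**Step 1: the two resume rules by baseline grade.** Let b be the baseline grade.
- Text rule (general Section 6 sentence): highest grade at which dosing may resume = max(1, b).
- Table rule (grade 3 and grade 4 hematologic rows): highest grade = 2 if b = 2, otherwise 1.

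| Baseline grade b | Text allows | Table allows | Same? |
|---|---|---|---|
| 0 | 1 | 1 | yes |
| 1 | 1 | 1 | yes |
| 2 | 2 | 2 | yes |
| 3 | 3 | 1 | no |
| 4 | 4 | 1 | no |

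The rules part only at baseline grades 3 and 4. There the table asks the patient to end up better than at entry, by 3 − 1 = 2 grades or 4 − 1 = 3 grades, before the next dose.

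**Step 2: does the gap reach enrolled patients?** This depends on how CTCAE v5.0 grades the entry counts in Section 3.1.1, and the protocol does not print the cut-points. If those counts graded as 2, the exception would cover them and these patients would face no conflict. If they grade as 3 or 4, as assumed here, the last two rows of the table apply. The difference between the two rules does not itself depend on the assumption.

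**Step 3: what happens if the table rule is not met.** Counting the delay from the due date of a 28-day cycle:
- Next dose due: cycle day 29.
- Day-42 marrow prompt: 42 − 29 = 13 days into the delay.
- 28-day limit: 29 + 28 = cycle day 57, which is 57 − 42 = 15 days after the prompt.

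The grade 4 row gives an action for that marrow only when it shows no MDS. If MDS is still present, the same row's hold and the 28-day footnote continue to apply, so the marrow step does not give the patient a way back to dosing at baseline.

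**Step 4: GI label.** In whole stools a day over baseline, grade 2 as printed covers values under 4, grade 3 covers 7 and above, and 4, 5 and 6 fall in no row. If the grade 1 label is also read as over baseline, which it does not say, then 1, 2 and 3 fit both a continue row and a hold row. If grade 1 is read as an absolute count, a rise of 4 to 6 still has no row beyond grade 1 to go to.

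**Step 5: neurological label.** The grade 2 entry describes moderate symptoms that limit instrumental daily activities. The grade 3-4 entry switches to creatinine and is identical to the renal grade 4 entry, which points to a copying error.

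**The case against.** The strongest reply is that the tables govern. Section 6 refers delays to its tables and points to specific guidance below, and general text followed by such pointers is naturally read as yielding to the tables. This largely stands. A reader might infer that nothing indicates which rule applies; the documents do not support that. What remains is that there is no explicit precedence clause, and that the table, if it does govern, contradicts the general rule while omitting baseline grades 3 and 4.

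A reader might also count three statements of the baseline rule against one table. Two of them cover only events meeting DLT criteria. Section 5.4 excludes hematologic toxicity attributed to active MDS from DLTs, and its grade 4 cytopenia DLTs require a marrow without MDS. For a patient whose marrow still shows MDS, those two sentences mostly do not apply, so the conflict rests on the one general sentence.

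Removal from therapy is not automatic. Section 5.2.2 allows a delay for toxicity of grade 3 or higher that the treating investigator thinks rules out dosing, so there is judgment at the start of a hold, and the overall PI can agree an exception. Both safeguards stand. The separate discussion with the PI about delays beyond 28 days does not help, because it is limited to non-toxicity events.

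On the labels, Section 6 names CTCAE v5.0 for grading, so a rise of 4 to 6 stools or a severe neurological event still receives a grade. This limits the harm, but the printed descriptors still contradict the grading that staff are told to use.

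**Conclusion.** Wrong as written, and minor. The hematologic rows and the general Section 6 text give different resume rules for a baseline worse than grade 2. The table, to which the text refers, can take a patient who has returned to the entry count off therapy after a 28-day delay, unless the overall PI or the treating investigator steps in. The two label errors are plain on the page.

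The number of patients affected is unknown and probably small: it takes a severe entry count, a hematologic hold, recovery only to baseline, and a site that applies the table without either safeguard. Section 2.2 lists possibly related grade 3 or higher thrombocytopenia in 4 and neutropenia in 2 of 26 single-agent patients with MDS or AML. That shows such holds are plausible, but it comes from a different population and does not estimate the number here.

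A reader might infer that lost treatment time weakens the primary analysis. The documents give no basis for that, and power and type I error are unaffected. The conclusion for enrolled patients rests on the assumption that the Section 3.1.1 entry counts grade worse than 2 under CTCAE v5.0.

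**What to change.** 1. In both the grade 3 and grade 4 hematologic rows, change the parenthesis to *(or to the patient's baseline, if baseline was grade 2 or worse)*. Redosing at a severe baseline is a clinical safety choice, so the investigator should confirm that this is intended. If the narrower rule is intended, state in the Section 6 text that the table governs for hematologic toxicity.
2. Relabel GI grade 2 as 4-6 stools/day over baseline.
3. In the neurological grade 3-4 row, replace the creatinine criterion with a neurological severity descriptor per CTCAE v5.0, in the style of the grade 2 entry.

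The cost is wording in four table cells (two hematologic, one GI, one neurological), with no new assessments and no additional patients.

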7. ADVERSE EVENTS: LIST AND REPORTING REQUIREMENTS

Adverse event (AE) monitoring and reporting is a routine part of every clinical trial. The following list of reported and/or potential AEs (Section 7.1) and the characteristics of an observed AE (Section 7.2) will determine whether the event requires expedited reporting **in addition** to routine reporting.

7.1. Expected Toxicities

Toxicities associated with MBG453 are based on prior experience with this drug used both as a single agent and in other chemotherapy combinations, in both solid tumors and in hematological malignancies, as presumed based on the current knowledge including the mechanism of action and the available pre-clinical and clinical safety data.

7.1.1. Potential immune mediated toxicities

Based on the reported experience, toxicity associated with MBG453 as single agent or in combination treatment is expected to include AEs of a potential immune-mediated etiology. Despite important clinical benefits, checkpoint inhibition is associated with a unique spectrum of side effects termed immune-related adverse events (irAEs) or, occasionally, adverse events of special interest. IrAEs include dermatologic, gastrointestinal, hepatic, endocrine, kidney, respiratory, neurological and other less common inflammatory events. IrAEs are believed to arise from general immunologic enhancement, and temporary immunosuppression with corticosteroids, tumor necrosis factor-alpha antagonists, hormone replacement or other agents can be an effective treatment in most cases.

In general, treatment of moderate or severe irAEs requires interruption of the checkpoint inhibitor and the use of corticosteroid immunosuppression. Treatment is based upon the severity of the observed toxicity.

Serologic, immunologic and histologic (biopsy) data should be used to support an irAE diagnosis. Appropriate efforts should be made to rule out neoplastic, infectious, metabolic, toxin, or other etiologic causes of the irAE.

7.1.2. Skin Toxicity

Twelve out of 133 patients (9%) and 18 out of 119 (15%) patients experienced skin related adverse events with MBG453 as single agent or in combination with PDR001 (PD1 inhibitor) in the solid tumor study, respectively. The majority of these AEs were Grade 1 or 2 and were manageable and reversible. One case of drug related rash maculopapular of Grade 3 was reported in MBG453 in combination with PDR001.

In the MDS/AML study, MBG453 was associated with skin related adverse events as follows: for single agent MBG453 (arm 4) in two out of 26 patients (8%), for MBG453 in combination with decitabine (arm 2) in seven out of 81 patients (9%), for MBG453 in combination with azacitidine (arm 6) in one out of 16 patients (6%), for MBG453 in combination with PDR001 (arm 5) in one out of 11 patients (9%), and for MBG453 in combination with PDR001 and decitabine (arm 3), no patients experienced skin related adverse events.

The majority of the AEs in the MDS/AML study were Grade 1 or 2 and were manageable and reversible. There was one case of Grade 3 drug related rash reported in Arm 2, one case of Grade 3 drug related rash reported in Arm 4 and one case of Grade 3 drug related rash reported in Arm 5.

Patients should be monitored carefully for any skin toxicity or mucositis. Specific guidance on management of skin toxicity includes discontinuation of study treatment for any suspected case of SJS/TEN.

7.1.3. Hepatotoxicity

Hepatic adverse events have been observed with MBG453 as a single agent and in combination. Abnormalities in hepatic enzymes are common in patients with cancer, who often have multiple possible etiologies for liver toxicities including concomitant medications, infections, liver metastases, obstruction, and prior hepatotoxic therapies.

Of the 133 patients treated with MBG453 single agent in the solid tumor study, 3 patients (2%) reported drug related AST increase and 1 patient (1%) reported drug related ALT increase. No grade 3 or grade 4 AST or ALT increase have been reported. Of the 119 patients treated with MBG453 and PDR001 combination, 7 patients (6%) reported drug related AST increase and 5 patients (4%) reported drug related ALT increase. Of these, 1 patient reported grade 3 AST elevation and 1 patient reported grade 3 ALT elevation. No cases of drug related bilirubin elevation were reported associated with AST and ALT elevation. Two serious cases of immune mediated hepatitis were reported from the combination study with PDR001 and considered as suspected to be related to study drug combination.

In the MDS/AML study, investigation related adverse events have been detailed by treatment arm. For patients treated with single agent MBG453 (arm 4), one patient experienced drug-related ALT increase (4%) and one patient experienced drug-related AST increase (4%), both of which were below grade 3. For MBG453 in combination with decitabine (arm 2), four patients (5%) experienced ALT increase (1 of these was a grade 3 drug related case) and 2 patients (3%) experienced AST increase (both of these were drug related and none were grade 3 or higher). For MBG453 in combination with azacitidine, one patient experienced drug related AST increase (6%) below grade 3. For MBG453 in combination with PDR001, there were no reported cases of drug related ALT or AST increase. For MBG453 in combination with PDR001 and decitabine, there were no reported drug-related grade 3 ALT increase, but 1 patient (5%) experienced drug related AST increase. In the MDS/AML study, no cases of drug related bilirubin elevation were reported associated with AST and ALT elevation.

Evaluation of patients with enzyme abnormalities should assess alternative possibilities to the extent possible before attributing the event to study treatment and initiating immunosuppressive therapy. Periodic monitoring of liver enzymes is required.

